NCT number	NAV-CMV-2019
Date	May, 2018
Study Title:	Pre-engraftment Cytomegalovirus DNAemia in allogeneic hematopoietic stem cell transplant recipients: incidence, risk factors and clinical outcomes
Request Date:	
Principal Investigator Contact Information	[name]
Name:	[name]
Title:	MD, PhD
Address 1	[name]
Address 2	
City, ST, Zip	[name]
Phone/Fax:	[name]
[contact]	
Institution Contact Information	INCLIVA, Institución de Investigación Sanitaria, Hospital Clínico de Valencia
Name:	INCLIVA, Institución de Investigación Sanitaria, Hospital Clínico de Valencia
Address 1	[name]
Address 2	
City, ST, Zip	[name]
Phone/Fax:	[name]
website	
Number of Subjects: 878	

## Background and Rationale

Cytomegalovirus DNAemia occurs frequently in allogeneic hematopoietic stem cell transplant (allo-HSCT) recipients [1]. Both high-level and persistent virus DNAemia are known risk factors for CMV end-organ disease and perhaps non-relapse mortality [2]. CMV DNAemia is usually documented after engraftment, but it may occur before. The virological features and clinical consequences of these latter early-onset episodes remain largely unexplored. The U.S. Food and Drug Administration (FDA) has recently approved letermovir for prophylaxis of CMV infection and disease in adult CMV-seropositive allo-HSCT recipients (PREVYMIS™, Merck & Co., New Jersey, USA). In accordance with the design of the phase III, double-blind trial [3] the drug may be administered as early as the day of transplant and no later than 28 days post-transplant. Nevertheless, the timing of drug inception should be contingent on the clinical impact of very early episodes of CMV DNAemia. In a recent work from our group (single-center study) [4] we found that a total 38 out of the 197 patients in our series developed CMV DNAemia before engraftment (cumulative incidence, 19%; 95% CI, 10-30.3%). Nine episodes of CMV DNAemia were detected prior to the time of donor progenitor cell infusion. A greater number of post-engraftment episodes required preemptive antiviral therapy compared with pre-engraftment episodes (62.5% vs 44.7%;  $P=0.05$ ). The cellular content of the donor progenitor cell infusion and transplant characteristics of patients did not differ between patients with pre- or post-engraftment CMV DNAemia. The cumulative incidence of overall mortality by days 100 and 365, aGVHD by day 100 and relapse by day 365 were not significantly different between patients with pre-engraftment or post-engraftment CMV DNAemia. Our study was limited by the retrospective and single-center design and the scarce number of pre-engraftment CMV DNAemia episodes included; therefore, the results may not be extrapolated to other transplantation centers or patient cohorts. Further retrospective and prospective studies are thus required to validate the data presented herein.

## Objectives

**1. Assess the incidence of pre-engraftment CMV DNAemia using highly sensitive real-time PCR assays in allo-HSCT**

**2. Evaluate its impact of pre-engraftment CMV DNAemia on the time to engraftment, overall mortality, and non-relapse mortality.**

### **Hypothesis**

**Very early episodes of CMV DNAemia have no impact on the occurrence of engraftment, overall mortality and non-relapse mortality.**

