### **Study Design/Clinical Plan**

This is a multicenter, retrospective, observational and single arm study which will include all consecutive allo-HSCT recipients at risk of CMV infection allografted from 1st January 2010 until 31th December 2019 in Spanish transplant centers belonging to the “Grupo Español de trasplante hematopoyético y terapia celular” (GETH group). No less than 10 centers performing bot related and unrelated allo-HSCT in Spain will participate in the study.

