**Analysis of the clinical impact of CMV DNAemia will be performed by evaluation of:**

- Time to engraftment
- Overall mortality

The analysis will be performed comparing the clinical impact of CMV DNAemia as described before, in relation to time of CMV DNAemia initiation in the following groups:

- Patients with DNAemia before engraftment vs after engraftment
- Patients with DNAemia before engraftment and before HSC infusion vs patients with DNAemia before engraftment after HCS infusion
- Comparison of time of initiation of CMV DNAemia from day -7 to HCS infusion on a weekly basis until engraftment.

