## Statistical Plans

**Non-parametric and semi-parametric analyses.** The probabilities of CMV DNAemia, CMV DNAemia requiring pre-emptive therapy, CMV-D, NRM and relapse will be estimated by the cumulative incidence method (marginal probability).

Competing events will be defined as follows; in the case of relapse, the competing event was NRM without the occurrence of the disease. For CMV DNAemia, CMV DNAemia requiring pre-emptive therapy, CMV-D and GVHD the competing event will be relapse or death without the event. For NRM the competing event will be relapse.

The assumption of proportional hazards over time will be tested for all explanatory covariates using a time-dependent covariate. CMV DNAemia, CMV DNAemia requiring pre-emptive therapy and CMV-D will be treated as time-dependent co-variates.

If time-dependent covariates are to be included in the final model multivariate analyses of mortality the analysis will be performed by Cox proportional hazards regression model, with inclusion of those variables with a P value less than 0.1 in the prior univariate testing.

If either, early or late CMV DNAemia (included individually as time-dependent covariates) are found to have an impact on OS in the univariate analysis, semi-landmark plot will be constructed to illustrate visually the effect.

Statistical analysis of the clinical impact of CMV DNAemia at different periods of time before engraftment will be performed as described previously for early or late CMV DNAemia

All statistical analyses will be performed using SPSS version 20 (SPSS, Chicago, IL) and R version 2.12.2 (The CRAN project) with the packages survival v2.36-10, Design 2.3-0, prolim v1.2.1 and cmprsk v2.2-221.

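### The hypothesis is one of no impact, but the plan has no bounds, confidence-interval rule or precision that could support it, and the P<0.1 screen does not clearly exempt early DNAemia

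*Combined protocol and SAP*

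**What the plan says.** The Hypothesis section reads "Very early episodes of CMV DNAemia have no impact on the occurrence of engraftment, overall mortality and non-relapse mortality". The second objective is worded neutrally: "Evaluate its impact of pre-engraftment CMV DNAemia on the time to engraftment, overall mortality, and non-relapse mortality".

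The section on clinical impact lists group comparisons by time of onset, the first being "Patients with DNAemia before engraftment vs after engraftment". Statistical Plans describes cumulative incidence estimates and a Cox model for mortality. CMV DNAemia is handled as a time-dependent covariate.

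The model-building sentence opens "If time-dependent covariates are to be included in the final model" and ends "with inclusion of those variables with a P value less than 0.1 in the prior univariate testing". A plot is to be drawn if early or late DNAemia "are found to have an impact on OS in the univariate analysis"; what counts as an impact is not defined. For NRM the plan says "For NRM the competing event will be relapse", but does not say whether a regression for NRM would be cause-specific or subdistribution. No regression for time to engraftment is described.

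The title table gives 878 subjects. No alpha, power, event count, smallest relevant effect or target precision goes with that number. The only confidence interval in the document (10-30.3%, Background and Rationale) is for incidence in the group's earlier series.

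**The concern.** A hypothesis of no effect is not supported by failing to reject it. It needs an interval narrow enough to exclude effects that would matter, and the plan never says which those are. As written, an absence of relevant effect and an estimate too imprecise to tell could be reported in the same words.

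This matters because Background and Rationale ties the timing of drug inception to the clinical impact of very early episodes. The same section says the earlier single-center study, which found no significant differences in several outcomes, was limited by its small number of pre-engraftment episodes. The new study is meant to improve on that, but has no rule that would prevent the same ambiguity.

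The P<0.1 screen could add to the problem. If it applies to early DNAemia, a result in line with the hypothesis would usually remove the exposure from the adjusted model. Only an unadjusted estimate from an observational cohort would then remain.

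**Working it through.** **Inputs from the document.** 878 subjects (title table); 38 of 197 with pre-engraftment DNAemia (Background and Rationale); screen at univariate P<0.1 (Statistical Plans). 38/197 = 19.3%, which agrees with the quoted 19%; 878 × 0.193 ≈ 169 exposed patients. The figure of 878 has no stated basis, so it cannot be reproduced.

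**Assumptions not in the document.** Two-sided 5% test; HR 1.3 as an example of a moderate effect; overall mortality 20-50% (176-439 deaths); NRM 10-25% (88-220 events); exposed versus all others, with a fixed exposure split.

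**Standard error.** SE(log HR) = 1/√(D·p·(1−p)), with p(1−p) = 0.193 × 0.807 = 0.1557.
- D = 176: 1/√27.4 = 0.191
- D = 439: 1/√68.3 = 0.121

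**Precision.** The 95% CI around an observed HR of 1 is about 0.69-1.45 with 176 deaths and 0.79-1.27 with 439.

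**Power for HR 1.3.** Φ(ln 1.3/SE − 1.96), with ln 1.3 = 0.2624.
- D = 176: Φ(1.373 − 1.96) = 28%
- D = 439: Φ(2.169 − 1.96) = 58%
- Simulation (Cox model, fixed split, 3,000 runs): 33% and 63%, so the formula is about 5 points low.
- Over 10-30.3% exposed, by formula: 18-71%
- NRM at 19.3% exposed, by formula: 16-34%

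**Screen, if applied to the exposure.** The chance of P≥0.1 is Φ(1.645 − t) − Φ(−1.645 − t), with t = ln(unadjusted HR)/SE.
- Unadjusted HR 1: 0.95 − 0.05 = 90%, whatever the sample size. A simulation with time-dependent exposure gave 90.2% (30% one-year mortality, 2,000 runs).
- Unadjusted HR 1.2: t = 0.954 gives 75% (176 deaths); t = 1.507 gives 55% (439 deaths)
- Unadjusted HR 1.3: 61% and 30%
- Adjusted HR 1 with confounding: 66% in one simulated scenario (binary confounder with mortality HR 2; exposure 27% versus 11%; 30% baseline one-year mortality)

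**What an equivalence rule could achieve.** For an 80% chance that the whole 95% CI lies within 1/B to B at a true HR of 1, B = exp((1.96 + 1.2816)·SE).
- Overall mortality: exp(3.2416 × 0.191) = 1.86 with 176 deaths; 1.48 with 439
- NRM: 2.40 with 88 events (SE 0.270); 1.74 with 220 (SE 0.171)
- For B = 1.3 the deaths needed are 3.2416²/(0.1557 × 0.2624²) ≈ 981, more than the 878 patients.

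Time-dependent coding and adjustment would generally widen these intervals; that loss is not quantified here.

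**The case against.** Three objections carry weight.

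First, the model-building sentence can be read the other way. The plan has just said that DNAemia is a time-dependent covariate, so the opening "If time-dependent covariates are to be included in the final model" may mean that DNAemia enters as that term and the screen selects the rest. A reader might infer that the plan will lose its main adjusted estimate nine times in ten. The document does not support that: the scope of the screen is unclear, and 90% holds only for an unadjusted HR of 1. In a cohort where confounding is expected, the share is lower if confounding moves the unadjusted HR away from 1. What stands is that a sentence controlling the main estimate has two readings.

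Second, the harm is inferred. The objective is to evaluate impact, the hypothesis may only express an expectation, and the univariate result merely triggers a plot. A reader might infer that a non-significant P will be reported as no impact; nowhere does the plan say so. It also says nothing that would prevent it.

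Third, once the aim is estimation with an adjusted HR and CI, bounds are largely optional. That is fair, and the fix asks for them only if a no-impact statement is still wanted.

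A reader might also conclude that 878 is too few. The document gives no event rates, so the power figures are illustrations. The study "will include all consecutive allo-HSCT recipients at risk of CMV infection", so its size is set by the available cohort.

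**Conclusion.** The point holds in a limited form. That the plan gives no bounds, interval rule or expected precision for a no-impact hypothesis is plain from the text and rests on no assumption. A non-significant result could not support the hypothesis as stated.

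The screen is a conditional problem. It arises only if the P<0.1 rule covers early DNAemia, and its size depends on the unadjusted HR: about 90% of studies without an adjusted estimate at HR 1 (two-sided test), and about 55-75% at HR 1.2 under the assumed 20-50% mortality. It concerns the mortality model only.

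The power range for HR 1.3 (28-58% by formula, 33-63% by simulation) shows that non-significance would be common even with a moderate effect. It depends on the assumed event rates and on the earlier single-center exposure share. The plan should be changed before analysis, but the data remain fully usable.

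**What to change.** 1. Reword the Hypothesis section as estimating the effect of early DNAemia, in line with the second objective.
2. In Statistical Plans, keep early DNAemia (time-dependent) in the adjusted models for overall mortality and NRM whatever its univariate P, and apply the P<0.1 screen only to the other covariates. Report the adjusted HR with 95% CI as the main result. For NRM, state whether it is cause-specific or subdistribution.
3. State that a non-significant P will not be reported as no impact. If such a statement is still wanted for overall mortality or NRM, fix lower and upper HR bounds before analysis and read the 95% CI as follows:
   - wholly within the bounds: no relevant impact;
   - excludes 1 and does not lie wholly within the bounds, including a CI wholly beyond a bound: association in its direction;
   - otherwise: inconclusive.
4. Make no no-impact statement on engraftment from the before- versus after-engraftment contrast, because group membership there depends on when engraftment occurs. This bars one misleading comparison; it does not supply an engraftment model, which the plan still lacks.

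The cost is wording and, if item 3 is used, one agreed pair of bounds per outcome. No extra patients or data are needed. The downside is that an inconclusive result is likely. At 19.3% exposed, the bounds attainable with 80% chance are about 1/1.86-1.86 to 1/1.48-1.48 for overall mortality (176-439 deaths) and 1/2.40-2.40 to 1/1.74-1.74 for NRM (88-220 events).

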### **Study Design/Clinical Plan**

This is a multicenter, retrospective, observational and single arm study which will include all consecutive allo-HSCT recipients at risk of CMV infection allografted from 1st January 2010 until 31th December 2019 in Spanish transplant centers belonging to the “Grupo Español de trasplante hematopoyético y terapia celular” (GETH group). No less than 10 centers performing bot related and unrelated allo-HSCT in Spain will participate in the study.

**Inclusion criteria include:**

- Recipients >18 years old
- CMV seropositive recipients and/or donors
- DNA load monitoring by real-time PCR starting from day -7 and conducted on a weekly CMV basis (0, +7, +14,...) at least until day +100
- First allo-HSCT
- T-cell replete allograft

Essential variables which include patients, donor and transplant's characteristics as well as post-transplant outcome will be retrieved from MED-A of PROMISE EBMT database.

Specific CMV data (including one-year longitudinal PCR results, date of onset and type of pre-emptive antiviral therapy as well as CMV disease data) will be retrospectively reported by each participating center.

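### Recipient serostatus is neither reported separately nor guaranteed in any model, so the incidence does not directly answer the letermovir question and the timing contrasts are at risk of confounding

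*Combined protocol and SAP*

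**What the plan says.** - **Eligibility.** The inclusion criteria accept "CMV seropositive recipients and/or donors". R+ recipients with any donor and D+/R- pairs are both eligible; only pairs with both members seronegative are excluded. This agrees with Study Design/Clinical Plan, which takes "all consecutive allo-HSCT recipients at risk of CMV infection allografted".
- **Rationale.** Background and Rationale describes letermovir as approved for "prophylaxis of CMV infection and disease in adult CMV-seropositive allo-HSCT recipients" and says that "the timing of drug inception should be contingent on the clinical impact of very early episodes of CMV DNAemia".
- **Incidence objective.** Objective 1 is to "Assess the incidence of pre-engraftment CMV DNAemia using highly sensitive real-time PCR assays in allo-HSCT". It is not limited to R+ recipients and not split by serostatus.
- **Timing contrasts.** The section on analysis of clinical impact compares DNAemia before and after engraftment, then "Patients with DNAemia before engraftment and before HSC infusion vs patients with DNAemia before engraftment after HCS infusion", then onset by week from day -7 until engraftment.
- **Adjustment.** Statistical Plans describes one multivariable analysis: a Cox model for mortality, taking variables with univariate P below 0.1. Serostatus is not named there or in the list of data to be retrieved. No adjustment is described for time to engraftment, although it is an outcome in Objective 2.

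**The concern.** Two separate questions arise.

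The first is whom the incidence describes. The rationale concerns the timing of a drug approved for seropositive recipients, and D+/R- patients are outside that group. A reader who wants the early-DNAemia risk in seropositive recipients will find only a pooled figure, which depends on the D+/R- share at the participating centres.

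The second is comparability of the timing groups. A seronegative recipient carries no latent CMV and has received no donor cells before infusion. Apart from misclassified serology or a false-positive PCR, there is then almost no source of DNAemia. The documents do not state this; it follows from what serostatus means. The before-infusion group is therefore almost entirely R+, while later groups can mix R+ reactivation with infection from the donor. If serostatus also affects engraftment or mortality, part of any difference between early and late DNAemia would reflect serostatus. If D+/R- patients fared worse, early DNAemia would look safer than it is and a real harm could be hidden, in a study whose hypothesis is no impact.

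**Working it through.** **Inputs from the documents.** Background and Rationale reports that "38 out of the 197 patients in our series developed CMV DNAemia before engraftment", given as 19% (95% CI 10-30.3%), and that "Nine episodes of CMV DNAemia were detected prior to the time of donor progenitor cell infusion". The title page gives 878 subjects.

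**Inputs assumed.** The documents do not give the D+/R- share (*f*), the D+/R- risk of pre-engraftment DNAemia (*r*), or a hazard ratio for D+/R- versus R+ (*g*). I use *f* = 5-20%, *r* = 0-5% and *g* = 1.25-2.

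**Step 1: the plan's own figure.** 38/197 = 19.3%, which agrees with the stated 19%.

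**Step 2: pooled versus R+ incidence.** If the 19% came from a pooled series, R+ incidence = (0.19 - *f r*)/(1 - *f*).

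| *f* | *r* | Calculation | R+ incidence | Gap to 19% (points) |
|---|---|---|---|---|
| 5% | 5% | (0.19 - 0.0025)/0.95 | 19.7% | 0.7 |
| 15% | 2% | (0.19 - 0.003)/0.85 | 22.0% | 3.0 |
| 20% | 5% | (0.19 - 0.010)/0.80 | 22.5% | 3.5 |
| 20% | 0% | 0.19/0.80 | 23.8% | 4.8 |

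For scale, the simple 95% half-width at N = 878 is 1.96 × √(0.193 × 0.807/878) = 2.6 points. The gap is below sampling error at the low end of the range and above it at the high end.

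**Step 3: before versus after infusion.** Both groups lie within pre-engraftment DNAemia. Assume that all nine pre-infusion episodes are among the 38, and that every D+/R- episode falls after infusion. The after-infusion group is then 0.19 × 29/38 = 0.145 of the cohort, and the D+/R- share of it is *q* = *f r*/0.145. With no true timing effect, the approximate spurious ratio of mean hazards (before/after) is 1/(1 - *q* + *q g*).

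- *f* = 15%, *r* = 2%: *q* = 0.003/0.145 = 2.1%; at *g* = 2 the ratio is 1/1.021 = 0.98.
- *f* = 20%, *r* = 5%: *q* = 0.010/0.145 = 6.9%; at *g* = 2 the ratio is 1/1.069 = 0.94.
- Less favourable assumption: D+/R- patients have half the R+ rate of after-infusion episodes and *f* = 20%. Then *q* = (0.2 × 0.5)/(0.8 + 0.2 × 0.5) = 11.1%, and at *g* = 2 the ratio is 1/1.111 = 0.90.
- At *g* = 1 the ratio is 1: there is no bias.

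**Step 4: before versus after engraftment.** Let *qE* and *qL* be the D+/R- shares in the early and late groups, both assumed. The spurious ratio is (1 - *qE* + *qE g*)/(1 - *qL* + *qL g*).

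| *qE* | *qL* | *g* = 1.25 | *g* = 2 |
|---|---|---|---|
| 0% | 5% | 0.99 | 0.95 |
| 2% | 10% | 0.98 | 0.93 |
| 5% | 15% | 0.98 | 0.91 |
| 0% | 20% | 0.95 | 0.83 |

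This contrast can be more exposed, because D+/R- infections that appear after engraftment all enter the late group.

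**The case against.** The strongest reply is that the plan never set an R+ estimand. Study Design/Clinical Plan defines a cohort at risk of CMV infection, Objective 1 asks for incidence in allo-HSCT generally, and letermovir appears only in the rationale. A reader might infer that the eligibility criterion is wrong, or that the pooled incidence is biased. The documents do not support that: for the cohort and objective as written, the pooled figure is the right quantity. This part of the reply stands.

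A reader might also infer that the timing contrasts are confounded as a matter of fact. That needs an effect of serostatus on engraftment or mortality, and the documents report none. In the earlier series, transplant characteristics did not differ between pre- and post-engraftment DNAemia. That is weak reassurance, since serostatus is not named and only 38 early cases were available, but it gives the stronger claim no support either. Patient and donor characteristics are to be retrieved, so the P < 0.1 screen could bring serostatus into the mortality model. It might equally fail to do so: with few D+/R- patients a real effect can miss the threshold, and nothing equivalent is described for time to engraftment.

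Finally, the size is uncertain. The serostatus mix behind the 19% is not given; if that series was all R+, Step 2 does not apply as written. The whole range of 19.7-23.8% also lies inside the stated interval of 10-30.3%.

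**Conclusion.** The point holds as a gap in analysis and reporting, of moderate weight, and not as an eligibility error. The plan pools R+ and D+/R- patients, ties its question to a drug for R+ recipients, and does not plan to separate the two or to guarantee adjustment.

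- **Incidence.** The pooled figure is valid but does not directly give the R+ figure. It would be about 1 to 5 points lower under the assumed shares and risks, provided that D+/R- risk is lower and the 19% series was pooled.
- **Timing contrasts.** There is a risk of confounding, conditional on an effect of serostatus on outcome. For the infusion contrast it is probably small: a spurious ratio of about 0.94-0.98 at an assumed hazard ratio of 2, or 0.90 under the less favourable assumption. For before versus after engraftment it may be larger, down to 0.83 in the most extreme case shown.

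A reader might go further and make R+ recipients the main population for every analysis. That would replace the estimand in the Objectives and the design section, and nothing in the documents requires it.

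**What to change.** Keep the inclusion criterion and the pooled incidence, and add to Statistical Plans:

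1. Report the cumulative incidence of pre-engraftment DNAemia by donor/recipient serostatus (D+/R+, D-/R+, D+/R-), and identify the R+ figure as the one relevant to letermovir.
2. Include recipient serostatus in the time-to-engraftment and mortality models for the timing contrasts, as a forced term or a stratum, whatever its univariate P value.
3. Restrict the before- versus after-infusion contrast to R+ recipients and describe D+/R- patients separately. Restriction is cleaner than regression here, because the before-infusion group has almost no D+/R- patients to compare.

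**Cost.** Additional analysis text and one extra model term. Serostatus must already be known to apply the inclusion criterion, so no new data are needed. The infusion contrast loses few patients: about 878 × 0.15 × 0.02 = 3 in the middle case and 878 × 0.20 × 0.05 = 9 at the upper end of the assumed shares and risks, all from the after-infusion group.

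### The PCR inclusion criterion has no exception for death, so applied as written it admits only patients who survive to day +100

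*Combined protocol and SAP*

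**What the plan says.** The Inclusion criteria list, alongside age, serostatus, first transplant and T-cell replete graft, a requirement for real-time PCR monitoring that starts at day -7 and is "conducted on a weekly CMV basis (0, +7, +14,...) at least until day +100". It is placed as a condition of entry. No text there or elsewhere limits it to patients still alive, or says that it describes a centre's surveillance policy and not the patient's completed monitoring.

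Four other places bear on how it should be read:

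- Study Design/Clinical Plan says the study is retrospective and will include "all consecutive allo-HSCT recipients at risk of CMV infection", from no fewer than 10 centres.
- Objectives asks for the effect of pre-engraftment DNAemia "on the time to engraftment, overall mortality, and non-relapse mortality".
- Statistical Plans defines competing events for CMV DNAemia, DNAemia needing pre-emptive therapy, CMV disease and "GVHD the competing event will be relapse or death without the event".
- The text after the inclusion list takes baseline data from the registry, "as well as post-transplant outcome will be retrieved from MED-A of PROMISE EBMT database", while the CMV data, "including one-year longitudinal PCR results", come retrospectively from each centre.

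**The concern.** A patient who dies on day +40 cannot have weekly PCR to day +100. Because the study looks back, survival to day +100 is already known when eligibility is judged. Taken at its word, the criterion therefore selects on an outcome of the study: every patient who enters is certain to be alive on day +100.

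The exposure of interest arises before engraftment, so the first 100 days are when an early effect on engraftment or death would show. Where the rule is applied literally:

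- mortality to day 100 is zero by construction, and later overall and non-relapse mortality are too low;
- patients who die before engraftment and before day +100 drop out of the time-to-engraftment analysis;
- any association with mortality describes only the period after day 100.

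Treating DNAemia as a time-dependent covariate, as Statistical Plans proposes, does not repair this, because it cannot bring back patients who were never entered.

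**Working it through.** **Inputs.** The document gives 878 subjects, with no derivation and no statement of whether that counts patients before or after eligibility is applied. It gives no mortality rates, so day-100 mortality (d100) and 1-year mortality (d365) are assumed in three pairs: 8/25%, 12/30% and 18/38%. The plan has no figure of its own on this point to reproduce.

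**Step 1: does the text contain an exception?** No. The consecutive-recipient design and the use of death as a competing event both presuppose that early deaths are in the cohort, but neither qualifies the criterion. The passages conflict if the criterion is applied as written.

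**Step 2: loss if every centre applied it literally.**

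Share of first-year deaths lost = d100 / d365.

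Apparent 1-year mortality = (d365 − d100) / (1 − d100).

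| Assumed d100 / d365 | First-year deaths lost | Apparent 1-year mortality |
|---|---|---|
| 8% / 25% | 8/25 = 32% | 17/92 = 18.5% |
| 12% / 30% | 12/30 = 40% | 18/88 = 20.5% |
| 18% / 38% | 18/38 = 47% | 20/82 = 24.4% |

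Apparent day-100 mortality is 0 in every row. If no centre applied the rule literally, the loss is 0 and the apparent rates equal the assumed ones.

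**Step 3: what happens to an early effect.** This is an illustration with all inputs assumed. Take 10% day-100 mortality in unexposed patients, a hazard ratio of 2 up to day 100 for patients with early DNAemia, and 15% mortality from day 100 to day 365 in both groups.

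- Exposed, day-100 mortality: 1 − 0.90² = 19%.
- Exposed, day-365 mortality: 1 − 0.81 × 0.85 = 31.1%.
- Unexposed, day-365 mortality: 1 − 0.90 × 0.85 = 23.5%.
- True difference: 0.3115 − 0.2350 = 0.0765, or about 7.7 points.
- Difference among day-100 survivors: 15% − 15% = 0.

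The illustration fixes exposure at transplant and compares exposed patients with all others. It is not the plan's comparison ("Patients with DNAemia before engraftment vs after engraftment") and should be read only as showing the mechanism.

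**The case against.** The best case on the other side is that the literal reading was never intended. The cohort is meant to be consecutive, death without the event is a competing event, and the group's own single-centre series, which this study is meant to validate, reported "The cumulative incidence of overall mortality by days 100 and 365". The criterion can also be read as describing a surveillance schedule, which a patient who died on day +40 followed while alive. The request for a year of PCR results carries no death clause either, and nobody would take it to exclude deaths within the year.

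Most of this stands as evidence of intent. It does not supply the missing words. The year of PCR results is a data item, whereas this is an entry rule, and an entry rule should not need other sections to rescue it.

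Three stronger readings are tempting, and the document supports none of them:

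- That early deaths were in fact excluded. No document shows that any centre did so.
- That centres applied the rule differently. Each centre reports its own CMV data and no common rule for early deaths is given, so this is possible, but nothing shows it happened.
- That the rule always biases the comparison towards the hypothesis of no impact. It does so for an effect confined to the first 100 days. A constant hazard ratio is preserved, and an effect confined to later follow-up is estimated correctly for that later period, though it would exceed an average over the whole first year. The problem is which period is being estimated.

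**Conclusion.** The concern holds as a defect in the eligibility text. Followed as written, the criterion conditions the cohort on day-100 survival and contradicts the consecutive-recipient design, the competing-event definitions and the engraftment and mortality objectives. The size depends on two things the document does not give: early mortality and how the rule was applied. Under the assumed rates, literal use everywhere would remove between about a third and a half of first-year deaths (32% to 47%) and take 6.5 to 13.6 points off 1-year mortality (25 − 18.5 and 38 − 24.4). If early deaths were kept throughout, as the other sections suggest, nothing is lost and only the wording needs correcting. I give no loss of power, because the plan states no effect size, power or event target to measure it against.

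**What to change.** Reword the criterion to require weekly PCR from day -7 until day +100 or death, whichever comes first, and state that no patient is excluded for dying before day +100. Keep the monitoring requirement for patients alive at day +100. An open-ended exception for end of follow-up would admit patients whose monitoring simply stopped, and would weaken detection of DNAemia.

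Ask each centre to check its list of consecutive recipients against the deaths recorded in MED-A, to supply the available PCR results for any early death that was left out, and to report the number excluded for incomplete monitoring, with reasons. State whether 878 is counted before or after these exclusions.

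The cost is a one-line change and a reconciliation at each centre. MED-A can identify omitted early deaths but does not supply their PCR results, so any centre that had left them out would have to retrieve those data itself. Reported mortality may then be less favourable.
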